
4) Pregnant women
 
5) Breast-feeding women
 
6) Patients with fructose intolerance
 
Sample size: 30 subjects
 
Rationale:
 
The primary outcome of this study is CAT reduction after taking Synatura®.
 
The margin of error was set at 3 points. Also, the standard deviation of the CAT score is reported to be 7.7 from the previous study (Int J Chron Obstruct Pulmon Dis. 2015;10:1623-1631). Assuming Alpha to be 0.05, beta 0.2, 25.307 subjects will be calculated. Assuming a drop rate of 0.15, 29.773 subjects will be required.

10. Study Period

From approval date of the study to 31 December 2018

11. Clinical Study Methods (including Dose, Treatment Method, Treatment Period and Concomitant Medications)

1) Overview
 
The clinical study on the effect of Synatura® will be conducted in COPD patients with symptoms of chronic bronchitis. The enrolled patients will be prescribed Synatura® following measurement of pre-dose pulmonary functions, quality of life and systemic inflammatory state. Pulmonary functions, quality of life and systemic inflammatory state will be repeatedly measured after taking Synatura® for 3 months, and the changes from pre-dose measurements will be observed.
 
2) Group: Single group
 
3) Study drug: Synatura® 15 mL TID for 3 months
 
Patients will be administered the above drug, and changes from pre-dose measurements will be observed.
 
① Changes from pre-dose measurement in pulmonary functions will be observed (FVC, FEV1, post bronchodilator FVC, FEV1).
 
② Changes from pre-dose scores in quality of life will be observed (COPD assessment test - CAT).
 
③ Changes from pre-dose measurement in systemic inflammatory state will be observed (CRP, fibrinogen, IL-6, TNF-a).

Item	At enrollment	After 3 months
Pulmonary functions	O	O
CAT	O	.O
BSS	O	O
CRP	O	.O
fibrinogen	O	.O
IL-6	O	.O
TNF-a	O	O

4) Prohibited concomitant medications

Xanthine derivatives (aminophylline, theophylline, choline theophyllinate, oxtriphylline), central nervous system stimulants (cocaine, amphetamine, codeine), antitussives and expectorants except for the study drug

5) Cost for procedures

In the case of pulmonary function test performed before and after treatment, it will be prescribed as a non-covered item and the actual cost of the test is paid the subject back.

6) Transportation cost

Patients participating in the study will be paid 50,000 KRW per visit.

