7) Cost for study drug

Synatura® will be prescribed for 3 months, and patients will receive the drug at the pharmacy in the study site. The cost for study drug will be paid from the research fund as a non-covered drug.

12. Observation Items/Clinical Test Items, Observation and Test Methods

1) Pulmonary functions - pulmonary function test will be performed before and 3 months after taking Synatura®.

2) Quality of life - CAT score and BSS will be performed before and 3 months after taking Synatura®.

3) Systemic Inflammation - blood samples will be taken before and 3 months after taking Synatura®, then stored and measured by ELISA in the laboratory.

13. Expected Side Effects and Precautions

According to the results of previous phase III studies, nausea, vomiting and dizziness can occur after taking Synatura®. Most of them are mild side effects and severe side effects that require medical interventions are not expected to occur. Currently, Synatura® is approved by the Ministry of Food and Drug Safety in March 2011, and widely used in clinical practice. In the 4-year post-marketing survey conducted in 606 patients for re-examination in Korea, the incidence of adverse events was reported to be 2.64% (16/606 patients, 16 cases) regardless of the causal relationship. No significant adverse events have been reported.

14. Discontinuation/Withdrawal Criteria
If the patient no longer wants to participate in the study
15. Evaluation Criteria, Evaluation Methods and Analysis Methods for Efficacy (Statistical Analysis Method)
The paired t-test will be used to establish the statistical significance of changes pre-dose measurement. 1) Changes from pre-dose measurement in pulmonary functions will be observed (FVC, FEV1, post bronchodilator FVC, FEV1). 2) Changes from pre-dose scores in quality of life will be observed (COPD assessment test - CAT). 3) Changes from pre-dose measurement in systemic inflammatory state will be observed (CRP, fibrinogen, IL-6, TNF-a).
16. Evaluation Criteria, Evaluation Methods and Reporting Methods for Safety (including Side Effects)

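### Does Section 15 leave BSS without an analysis and CAT without its place as the primary outcome?

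*Protocol*

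**What the plan says.** The primary outcome is named in the sample-size rationale, just before Section 10: "The primary outcome of this study is CAT reduction after taking Synatura". The calculation there uses CAT figures only.

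The Section 11 schedule marks BSS at enrollment and after 3 months. Section 12 places it beside CAT: "Quality of life - CAT score and BSS will be performed before and 3 months after taking Synatura".

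Section 15 opens with one general sentence on method: "The paired t-test will be used to establish the statistical significance of changes pre-dose measurement". Three numbered items follow:

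- lung function: "Changes from pre-dose measurement in pulmonary functions will be observed (FVC, FEV1, post bronchodilator FVC, FEV1"
- quality of life: "Changes from pre-dose scores in quality of life will be observed (COPD assessment test - CAT"
- inflammation: "Changes from pre-dose measurement in systemic inflammatory state will be observed (CRP, fibrinogen, IL-6, TNF-a"

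The list ①–③ in Section 11 has the same content. Neither list mentions BSS, and neither labels any endpoint as primary.

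**The concern.** Two things look wrong.

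First, both lists are itemised down to single spirometry measures and single markers, so they read as complete. BSS is the only efficacy item in the schedule that they omit. Read strictly, a score collected twice in up to 30 patients has no stated analysis, and a reader of the results could not tell whether a reported BSS change had been planned.

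Second, Section 15 is where one looks for the test that carries the efficacy conclusion. It puts lung function first and gives CAT no special standing. The visible part of the Section 6 objective speaks of clinical efficacy without naming an endpoint. In a single-group, open-label study, the worry is that whichever change reached significance would be offered as proof of efficacy.

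**Working it through.** **1. Where the endpoints appear**

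| Endpoint | Section 11 schedule | Section 12 | Lists in Sections 11 and 15 | Sample-size rationale |
|---|---|---|---|---|
| CAT | both visits | both visits | yes | primary outcome |
| BSS | both visits | both visits | no | not mentioned |
| Lung function | both visits | both visits | yes (4 changes) | not mentioned |
| Inflammatory markers | both visits | both visits | yes (4 changes) | not mentioned |

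Section 15 lists 4 + 1 + 4 = 9 changes; BSS would be a tenth. The BSS mismatch is confirmed. It lies between the two lists on one side and the schedule and Section 12 on the other. On the primary outcome there is no mismatch: one place names it and the others are silent.

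**2. Which endpoint the sample size rests on**

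Inputs from the rationale: margin 3 CAT points, SD of CAT 7.7, alpha 0.05, dropout 0.15.

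- (z₀.₉₇₅ × SD / margin)² = (1.95996 × 7.7 / 3)² = 25.307, the stated figure.
- 25.307 / (1 − 0.15) = 29.773, the stated figure, rounded up to 30.

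Both figures reproduce from CAT inputs alone, so the design treats CAT as the one endpoint that sets the size. This formula does not use the stated beta of 0.2. That is a separate matter and has no bearing on which endpoint is primary.

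**3. The false-positive chance under each reading**

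- No primary outcome, nine independent tests at 0.05: 1 − 0.95⁹ = 0.370.
- The same with BSS as a tenth: 1 − 0.95¹⁰ = 0.401.
- Nine tests with an assumed equal correlation (simulated): 0.33 at 0.3, 0.27 at 0.5, 0.20 at 0.7, 0.12 at 0.9. FVC and FEV1 before and after bronchodilator can be expected to be correlated, so 0.370 is an upper illustration.
- CAT as the single primary outcome, as the rationale states: 0.05.

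The first three lines require the designation in the rationale to be disregarded. The last describes the protocol as written.

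**4. What an analyst would do with BSS**

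BSS is measured before treatment and at 3 months in the same patients, like every other item, and Section 12 files it under quality of life with CAT. The general method sentence in Section 15 is a paired comparison with the pre-dose value. Applying it to BSS needs no new method, visit or data, and BSS is non-primary because the primary place is taken.

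**The case for a change.** The strongest case for a change is that the protocol disagrees with itself on BSS, and this does not depend on any unseen analysis plan. The lists are specific enough to be read as exhaustive, so BSS could be dropped or added once the data are known. Naming the primary outcome only in a sample-size paragraph is also untidy, and the efficacy section is where it belongs. The correction would cost a few lines.

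The inconsistency stands as a fact. Its consequence is limited, because the schedule and Section 12 put BSS on record as a planned before-and-after measurement, so leaving it out of the report would be visible to anyone holding the protocol.

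The multiplicity part does not stand. Saying once that CAT is primary is enough in a protocol this short; list order is not ranking, and Section 15 gives no other endpoint primary status. Claiming efficacy from a marker or a spirometry change would depart from the stated primary outcome. Whether the secondary results are reported with p-values or intervals, and how they are labelled, is commonly settled in a statistical analysis plan, which is not at hand here. Part of the text between Section 6 and the sample size is also not available, so it cannot be said that the protocol nowhere ranks its other endpoints.

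**Conclusion.** No change is needed. The error rate for the primary claim is 0.05 on the single CAT test; the figures of 0.37 and 0.40 do not describe this protocol. What remains is one non-primary score missing from two parenthetical lists, a gap that analysts fill with the same paired comparison used for everything else. Adding BSS to the lists would be tidier, but it would not alter the CAT analysis, the sample size of 30 or the conclusion the study can draw.

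This rests on two assumptions: that the designation of CAT in the sample-size rationale is honoured when results are reported, and that BSS and the eight other non-primary changes are read as supporting evidence.

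### Does Section 15's paired t-test throw away power for CRP, IL-6 and TNF-a by ignoring their likely skew?

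*Protocol*

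**What the plan says.** Section 15 gives one analysis rule: "The paired t-test will be used to establish the statistical significance of changes pre-dose measurement". Three groups of measurements follow it: lung function, CAT, and the inflammatory markers, for which it says "Changes from pre-dose measurement in systemic inflammatory state will be observed (CRP, fibrinogen, IL-6, TNF-a". It does not say whether marker values are analysed as measured or after a log transformation. Section 12 adds that "blood samples will be taken before and 3 months after taking Synatura®, then stored and measured by ELISA in the laboratory", so each patient contributes one pair of values per marker.

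The protocol gives no mean, SD, distribution, pre/post correlation, expected effect or power for any marker. The sample size rationale, just before Section 10, concerns CAT alone: "The primary outcome of this study is CAT reduction after taking Synatura".

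**The concern.** Section 15 applies the same test to a questionnaire score, lung volumes and blood concentrations. The natural reading is a difference in original units, 3-month value minus baseline. If CRP, IL-6 and TNF-a have long right tails, a few patients with high values dominate both the mean change and its SD. A treatment that lowers every patient's value by the same proportion is then harder to detect on the raw scale than on the log scale.

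The trial is small and a log-scale analysis costs a sentence, so it looks as if information on three markers is being given away. A false claim is not the worry. With no true change and equal spread at both visits, the raw test under strong log-normal skew is slightly conservative (about 3 to 4% two-sided, against about 5% on the log scale).

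**Working it through.** **1. Number of pairs.** Inputs from the sample size rationale: margin 3 points ("The margin of error was set at 3 points"), CAT SD 7.7, alpha 0.05, dropout 0.15.

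- n = (z × SD / margin)² = (1.95996 × 7.7 / 3)² = 25.307, as stated: "Assuming Alpha to be 0.05, beta 0.2, 25.307 subjects will be calculated".
- 25.307 / (1 − 0.15) = 29.773, as stated: "Assuming a drop rate of 0.15, 29.773 subjects will be required". The plan rounds this to 30.
- Expected completers: 29.773 × 0.85 = 25.307, so about 25 pairs.

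These figures come from CAT and do not depend on how the markers are analysed. (Beta does not enter this formula. That is a separate matter.)

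**2. Assumptions the documents do not supply.** Marker values log-normal, log-SD σ of 0.8 to 1.2, pre/post correlation ρ of 0.3 to 0.7, the same σ at both visits, one common proportional fall, two-sided 5% test.

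**3. Log-scale power in one cell.** The log difference has SD σ√(2(1 − ρ)). With σ = 1.0 and ρ = 0.5 this is 1.0. A 40% fall is ln 0.6 = −0.511, so the noncentrality is 0.511 × √25 / 1.0 = 2.55. With 24 degrees of freedom, power is 69%. Simulating the raw test in the same cell (40,000 trials) gives 45%, a loss of 24 points. For a 20% fall the figures are 19% and 11%.

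**4. The whole assumed grid, n = 25.** Loss of the raw test against the log test:

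- 40% fall: 10.4 to 35.4 points
- 20% fall: 4.9 to 12.8 points

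So the concern's arithmetic reproduces on this grid.

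**5. Just outside the grid, 40% fall.**

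| Setting | Loss of raw test (points) |
|---|---|
| σ = 0.5, ρ = 0.3 to 0.7, n = 25 | 0 to 2 |
| σ = 0.8, ρ = 0.8, n = 25 | about 4 |
| σ = 0.8, ρ = 0.7, all 30 complete | about 7 |
| σ = 1.2, ρ = 0.8, n = 25 | about 37 |

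The figures of 10 to 35 points describe one grid. They are not bounds.

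**6. Unequal spread.** Log-normal, baseline σ = 1.0, ρ = 0.5, n = 25; falls are falls in the median. Power, raw/log:

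| Follow-up σ | 40% fall | 20% fall |
|---|---|---|
| 0.7 | 81% / 79% | 37% / 23% |
| 0.85 | 65% / 74% | 22% / 21% |
| 1.2 | 22% / 59% | not run |

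If spread narrows to 0.7, the raw test is at least as good. The reason is that the two tests have different targets. A log-normal mean is median × exp(σ²/2), so narrowing from 1.0 to 0.7 multiplies the mean by exp((0.49 − 1.00)/2) = exp(−0.255) = 0.775 even when the median is unchanged. In that null-median case the raw test rejects about 9% and the log test about 5%. If instead the arithmetic means are equal, the raw test rejects about 7% and the log test 28%.

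**7. Another skewed shape.** For gamma-shaped values with the same coefficients of variation (0.95, 1.31, 1.79), ρ = 0.5 and a 40% fall, raw/log power is 66/54, 35/25 and 17/11%. The log test now loses 6 to 12 points on these rounded figures, and 4 to 14 over ρ = 0.3 to 0.7.

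**8. Section 15 against the log-scale alternative.** The alternative is a paired t-test on log values. Section 15 calls for a paired t-test on change from pre-dose. The first is an instance of the second, so it would complete the sentence without contradicting it.

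**The case for a change.** The best case for the concern is that Section 15 is the statistical method section and does name a test, so it is not simply silent. A reader would take change from pre-dose to mean original units. Samples are stored before assay, so the scale could be settled before any marker result exists, which would also prevent choosing it after seeing the data. On the assumed grid the loss is sizeable and keeps its direction: with all 30 patients it is still 6.9 to 36.6 points for a 40% fall.

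Part of this stands. The arithmetic is correct under its assumptions, and fixing the scale before assay is good practice. But naming the paired t-test settles the test and not the scale, and settling the scale of a non-primary marker is ordinary SAP content. No SAP was available here, so its absence from the protocol cannot be counted as a gap. Nor is the log scale a plain improvement. It replaces an absolute mean change with a ratio of geometric means, and which scale has more power depends on a distribution the protocol does not describe.

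**Conclusion.** The concern does not hold. Section 15 states nothing wrong about the markers, contradicts nothing elsewhere in the protocol, and does not fix an untransformed analysis.

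The possible cost of a raw-scale analysis is about 10 to 35 power points for a 40% fall and 5 to 13 for a 20% fall. That holds only with 25 pairs, log-normal values, log-SD 0.8 to 1.2, correlation 0.3 to 0.7 and equal spread at both visits, none of which except the approximate number of pairs comes from the documents. Mild skew leaves almost no difference for a 40% fall, and narrowing spread or a gamma shape can favour the raw test.

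The choice between scales is therefore a trade-off about the target of estimation for non-primary measures. The CAT result, the sample size and every stated figure are the same either way.

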Side effects evaluation criteria and evaluation methods - in the investigator's opinion, severity based on CTCAE 4.0, relationship to study drug and actions will be determined. Reporting adverse events Suspected unexpected serious adverse reactions will be reported to IRBs immediately. Suspected unexpected serious adverse reactions will be reported within following timeframe: ① Causes death or be life-threatening: within 7 days ② For other suspected unexpected serious adverse reactions: within 15 days.
17. Agreement on Compensation for Victims
1) For the safe characteristics of Synatura®, which will be administered in this study, it is considered that the risk to a victim is extremely low. 2) Any serious adverse events or unexpected problems should be reported to IRBs immediately (within 24 hours). 3) In case of damage due to participation in the study, study staffs will be notified and patients will be received urgent emergency treatment by staffs from Department of Pulmonology and Allergy. It will also be reimbursed under the responsibility of the principal investigator for all medical problems that arise. 4) Insured for compensation.
18. Care and Treatment Criteria for subjects after the Study
After the end of the study, patients may continue to take Synatura® or discontinue. After the end of the

study, continuation of taking Synatura® will be decided by the investigator based on the patient's symptoms (cough and sputum).

19. Measures to Protect the Safety of Subjects

- 1) Voluntary consent will be obtained from the subject based on sufficient explanation and understanding of the study.
- 2) Personal identification number (resident registration number, case number, name) of the subject will not be collected.
- 3) Extracted information will be safely stored for 5 years to prevent leakage, and discarded completely.
- 4) After extracting the data, the patient ID will be used after substituting with an alternative key. Access to the file will be limited to the person in charge of the study conduct and analysis

20. Other Necessary Details for safe and scientific implementation of Study

In case of damage due to participation in the study, study staffs will be notified and patients will be received urgent emergency treatment by staffs from Department of Pulmonology and Allergy.

Attachments: Informed Consent Form, Case Report Form Two references

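### Do the three reporting times for serious events in Sections 16 and 17 contradict each other?

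*Protocol*

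**What the plan says.** Three sentences in the protocol set times for reporting serious events.

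- Section 16 (safety evaluation and reporting), first sentence on timing: "Suspected unexpected serious adverse reactions will be reported to IRBs immediately". It names the recipient but gives no hours or days.
- Section 16, next sentence, same class of event: "Suspected unexpected serious adverse reactions will be reported within following timeframe: ① Causes death or be life-threatening: within 7 days", followed by "② For other suspected unexpected serious adverse reactions: within 15 days". It gives days but names no recipient and does not say when the clock starts.
- Section 17 (compensation), item 2: "Any serious adverse events or unexpected problems should be reported to IRBs immediately (within 24 hours". It covers a wider class, names the recipient and gives a figure.

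No sentence links the two sections. In the text available, the IRB is the only recipient named for a safety report. The Ministry appears as the approving authority, and the sponsor is not named as a recipient.

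**The concern.** Every suspected unexpected serious adverse reaction is also a serious adverse event, so one such reaction falls under all three sentences. Read in order, the 7/15-day sentence can look like the timetable for the sentence before it. On that reading the IRB is to be told immediately, within 7 or 15 days, and within 24 hours.

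The 24-hour statement is also the only one that covers serious events that are expected or unrelated to the drug, and it stands under a heading about compensation. Someone who relied on Section 16 alone might take 7 or 15 days as the meaning of immediately, and would find no time for the other serious events. At stake is how soon the IRB hears of a serious event.

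**Working it through.** No sample size, power or event count enters this point, so the check is a comparison of the text.

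**Inputs, side by side**

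| Place | Event class | Recipient | Time |
|---|---|---|---|
| Section 16, first timing sentence | Suspected unexpected serious reactions | IRBs | Immediately, no figure |
| Section 16, second timing sentence | Same class, fatal or life-threatening | Not named | 7 days = 7 × 24 = 168 hours |
| Section 16, second timing sentence | Same class, all others | Not named | 15 days = 15 × 24 = 360 hours |
| Section 17, item 2 | Any serious adverse event or unexpected problem | IRBs | Immediately, given as 24 hours |

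**Step 1: the sentences that name the IRB.** The first and last rows share recipient and adverb, and the last row's class contains the first row's class. Section 17 supplies the figure that Section 16 leaves out. These two do not conflict.

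**Step 2: the 7/15-day sentence, if it means the IRB.** All the limits then apply to one report, and they are upper limits. Since 24 < 168 < 360 hours, a report made within 24 hours is inside every one of them. The sentences are untidy together, but they can all be met by one action.

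**Step 3: the 7/15-day sentence, if it means another body.** The IRB report is governed by Step 1, and the 7 or 15 days govern a separate report. There is then no conflict. The only defect is that the recipient is not named.

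**Step 4: serious events outside that class.** Section 16 gives them no time. Section 17 item 2 does, with a recipient and a figure. They are covered, though not where one would look first.

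**Step 5: the worst misreading.** A reader who took the day counts as the IRB deadline and never reached Section 17 could report up to 7 − 1 = 6 days, or 15 − 1 = 14 days, after the Section 17 limit. To do so, that reader would also have to disregard the sentence just before the day counts, which already says that the IRB is told immediately.

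**Step 6: reach into the analysis.** The planned 30 subjects, the change in CAT score and the paired t-test in Section 15 use none of these times. The number of reactions affected cannot be computed, because the protocol gives no rate for suspected unexpected serious reactions. The Section 13 survey figure, 16/606 = 2.64%, counts adverse events of any kind and cannot stand in for it.

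**The case for a change.** The strongest case for a change is that either reading leaves a defect. If the recipient is the IRB, the day counts sit badly beside immediately and 24 hours. If it is another body, the protocol sets a deadline without saying to whom. Reporting recipients and deadlines are rules of conduct, not matters that a protocol leaves to a statistical analysis plan, and the sentences read as complete, so this is not a redaction. The comfort that 24 hours satisfies everything depends on the reader finding Section 17, which is headed as a compensation agreement. The repair would cost a short wording amendment and no patients or visits.

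Part of this stands. The recipient of the 7/15-day reports is missing, and the text does not settle which reading is meant. The rest is weaker. Section 17 follows directly after Section 16 in a short protocol, so where item 2 is placed is a matter of layout. Section 16 itself already says that the IRB is told immediately.

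Section 13's remark that "severe side effects that require medical interventions are not expected to occur" could be used to argue that nearly any serious reaction would count as unexpected. But severe and serious are different terms, and the protocol defines no threshold for unexpected. The inference is also unnecessary, since the overlap exists without it.

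**Conclusion.** The concern does not call for a change to the plan. The one certain defect is a clerical omission: the 7/15-day sentence in Section 16 names no recipient. The statements that do name the IRB agree with each other, serious events outside the unexpected-reaction class are covered by Section 17 item 2, and the three sentences can be met together on either reading.

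The effect on the sample size, the primary outcome and the efficacy analysis is nil. The effect on reporting is limited to a reader who stops at the day counts, passes over the sentence before them and does not reach Section 17. How often a reaction of this class would occur among 30 subjects cannot be said from the protocol.

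This conclusion assumes that site staff read Sections 16 and 17 together. It takes no view on which time is right. Stating the recipient and reconciling the sentences would be good housekeeping if the protocol were amended for another reason, but no result or conclusion of the trial depends on it.
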